PART B STUDY DESCRIPTION

TITLE OF PROTOCOL	Seizure-like Hippocampal Activity in Alzheimer's Disease Neurodegeneration		
Principal Investigator	[name].		
Co-Investigators	[name]; [name]; [name]		
Mailing Address	[name]		
E-Mail Address	[contact]		
P.I.'s Telephone	[name]	P.I.'s Pager [name]	Fax: [name]
Sponsor/Funding Source	Fidelity Biosciences Research Initiative; Neurology Department internal funding		

B1. PURPOSE OF PROTOCOL

To test the hypothesis that increased hippocampal perfusion on arterial spin labeling MRI in patients with Alzheimer's Disease (AD) is partially driven by focal epileptiform activity, and that this abnormal activity contributes to memory dysfunction.

Here we propose applying an imaging technique, arterial spin labeling MRI (ASL-MRI), ideally suited for testing this hypothesis. We will utilize a pharmacological probe, levetiracetam, to test whether sub-clinical epileptiform activity is driving increases in hippocampal perfusion and contributing to the declarative memory impairment in AD. Levetiracetam is an antiepileptic drug (AED) that inhibits epileptiform activity. Levetiracetam inhibits burst firing without affecting normal neuronal excitability. We will study patients with mild AD in three sessions, counterbalanced for order, in a crossover design. In each session, participants will undergo a baseline electroencephalogram (EEG). They will then be given either a placebo or intravenous levetiracetam low dose (2.5 mg/kg) or high dose (7.5 mg/kg). After drug administration, repeat EEG, ASL-MRI perfusion imaging, and behavioral testing will be conducted. Participants will return at 1-2 week intervals for the second and third sessions in the other conditions (levetiracetam low dose / levetiracetam high dose / placebo). This study will test whether increased hippocampal perfusion in AD is caused by epileptiform activity, whether this activity is contributing to memory impairment, and whether antiepileptic medications might be a new avenue of treatment in AD. If validated, ASL-MRI would be an ideal tool to non-invasively determine whether antiepileptic medications are effective in decreasing aberrant excitatory activity in the hippocampus in AD.

Aim 1: To determine whether increased hippocampal perfusion in AD is caused by epileptiform activity.

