Twenty subjects with mild AD (MMSE≥20) will participate in this study in the Clinical Research Center at Beth Israel Deaconess Medical Center. Subjects will be screened to ensure they meet inclusion and exclusion criteria and will provide written informed consent before any study procedures are performed. Each eligible subject will undergo three sessions, held 1-2 weeks apart, in a double blind, within-subject crossover design, counterbalanced for order (placebo / levetiracetam 2.5 mg/kg / levetiracetam 7.5 mg/kg), Figure 3. During each session, placebo or levetiracetam will be administered intravenously over 20 minutes. Drug administration will occur during EEG recording so that neurophysiological recordings can be acquired before, during, and after administration. Changes in EEG background frequency and level of synchrony will be analyzed⁴⁴⁻⁴⁶. After drug administration and EEG recording, hippocampal perfusion and functional connectivity will be measured with ASL-MRI and resting BOLD fMRI. Finally, participants will undergo a cognitive battery with memory tests particularly sensitive to hippocampal function (declarative memory, attention, working memory and executive function).

[figure not shown]

Figure 3. Overall paradigm. Participants will undergo testing in 3 sessions counterbalanced for order, with placebo, low dose LEV or higher dose LEV. Drug will be administered intravenously during EEG recording. Imaging will be acquired with anatomical, perfusion and resting state bold MRI. Cognitive testing will be performed with a battery including a memory test particularly sensitive to hippocampal function as well as other tests of frontal function.

2. Study Rationale

This protocol has three primary goals: to test the hypothesis that increased hippocampal perfusion in AD is at least partially driven by epileptic activity, that lowering epileptic activity may improve cognitive performance, and that perfusion MRI can be used as a non-invasive assay of the effects of medications that decrease epileptic activity in AD.

3. Subject Recruitment and Screening

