We plan on testing twenty AD participants (> age 50 years) meeting the NINCDS-ADRDA criteria for probable AD from the Cognitive Neurology Unit at BIDMC. All participants will have mild AD by the Mini-Mental Status Examination (MMSE \geq 20). The P.I., who specializes in neurodegenerative disorders, maintains an active clinic and treats over 100 patients with AD. In addition, the Cognitive Neurology Unit has over 13,000 patient visits per year.

Exclusion criteria include a history of seizures prior to the onset of AD, current use of an antiepileptic medication, current use of a medication known to lower seizure threshold (e.g. bupropion or a neuroleptic), presence of parkinsonism, significant cerebrovascular disease, other CNS disease or major depression. Subjects will be screened for depression with the Geriatric Depression Scale and excluded if they score greater than 9⁴⁷. Participants receiving standard treatments for dementia including cholinesterase inhibitors, memantine and serotonergic selective reuptake inhibitors may participate.

4. Crossover Design, Randomization, and Blinding

This is a within-subject, crossover study. Each subject will receive one of 3 study drug regimens at each session:

- Placebo
- Low dose levetiracetam (2.5 mg/kg)

c. High dose levetiracetam (7.5mg/kg)

A computer-generated, blocked randomization list will be generated that will randomly assign subjects to one of 6 groups. The order of drug administration will be counterbalanced to avoid pitfalls of the crossover repeated measures design.

- Group 1: A, B, C
- Group 2: A, C, B
- Group 3: B, A, C
- Group 4: B, C, A
- Group 5: C, A, B
- Group 6: C, B, A

The BIDMC research pharmacy will provide for randomization and blinding. Patients and investigators will be blinded to study group.

5. Study Procedures

Details and timing of the study procedures are listed below in the section "Study Plan".

- a. Demographics and baseline characteristics
- b. Medical history
- c. Neurologic history, including date of onset and progression of AD, history of prior seizures, and history of other neurological disorders.
- d. Recent and concomitant medications
- e. Assessment of renal function (blood urea nitrogen and creatinine)
- f. Vital signs
- g. At screening and at each visit: Systolic and diastolic blood pressure, heart rate, and respiratory rate; weight

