Participants will undergo declarative memory testing with the Free and Cued Selective Reminding Test, a task that is particularly sensitive to hippocampal function ⁴⁸. In addition, a short battery will be administered to test executive function, naming, visuospatial ability and semantic function (Trail Making Test Parts A+B, Phonemic fluency Test, Boston Naming Test 15-item version, clock drawing, category fluency). The primary endpoint for memory testing will be the free recall score from the Free and Cued Selective Reminding Test. This battery is fairly brief (30 min) but sensitive to both hippocampal function and changes in other cognitive realms impaired in AD.

p. Adverse events observed by investigator or reported spontaneously by the subject

6. Study Plan

The following assessments and procedures will be done at each study visit:

a. Screening visit

1. Informed consent
2. Demographics and baseline characteristics
3. Medical history
4. Neurologic history
5. Recent and concomitant medications
6. Blood collection for blood urea nitrogen and creatinine)
7. Vital signs: Systolic and diastolic blood pressure, heart rate, and respiratory rate; weight
8. Physical exam
9. Neurological exam
10. Mini-Mental Status Examination

b. Visits #1-3 (identical procedures, visit length 5-7 hours)

1. Vital signs: Systolic and diastolic blood pressure, heart rate, and respiratory rate; weight
2. Physical exam
3. Neurological exam
4. IV catheter placement
5. EEG (60 minute recording)
6. Study drug infusion (20 minutes)
7. Vital signs at 10, 20, 30 minutes after infusion
8. Imaging paradigm (60 minutes)
9. Behavioral testing (60-90 minutes)
10. Adverse events

There will be scheduled breaks between tests and scheduled lunch

c. Telephone follow-up

1. Follow up for adverse effects

B. Statistical Considerations

Sample Size Justification:

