We plan to study 20-25 subjects at BIDMC. We anticipate screening 25 subjects to enroll and randomize 20 eligible subjects. We have performed a power calculation based on our previous study finding hyperperfusion of the hippocampus in AD as compared to controls ²³. With a sample size of 20 AD participants, we will have a 72% probability of detecting a decrease in perfusion after levetiracetam, assuming administration of the drug lowers hippocampal CBF only to normal levels. This estimate is likely overly conservative for two reasons. First, the within subject design should markedly decrease variance. Second, if epileptiform discharges are contributing to hippocampal hyperperfusion and damage, then briefly ceasing the abnormal activity with drug should reveal underlying hypoperfusion like that typically seen in temporal lobe epilepsy.

Data Analysis:

The primary study outcomes are:

- Differences in hippocampal perfusion on ASL-MRI
- Differences in memory performance

The secondary study outcomes are:

Differences in whole brain regional cerebral blood flow on ASL-MRI
Differences in working memory and executive functions
Differences in EEG measures (alpha peak power, beta band power, delta/theta band power, coherence)

Behavioral Data

Measures of memory encoding, retrieval and storage will be analyzed using repeated measures ANOVA. We will test our a priori main hypothesis of improved memory performance after drug. In a secondary analysis, we will measure effects of drug on working memory and executive functions in a similar manner.

Imaging Data

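### The primary memory endpoint is measured at three visits 1-2 weeks apart, but the plan specifies neither parallel word lists nor a visit term in the memory model

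*Combined protocol and SAP*

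**What the plan says.** All references are to the combined protocol and SAP.

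- **Endpoint.** Section B3.B, Data Analysis, lists "Differences in memory performance" as the second of two primary outcomes. Section B3.A.5, item o (Behavioral testing), defines it: "The primary endpoint for memory testing will be the free recall score from the Free and Cued Selective Reminding Test". No form or list version is named.
- **Repetition.** Section B3.A.1: "Each eligible subject will undergo three sessions, held 1-2 weeks apart". Section B1 gives the same spacing. Section B3.A.6 heads the schedule "Visits #1-3 (identical procedures, visit length 5-7 hours" and includes behavioral testing at each of these visits. The screening visit includes the MMSE but not the word-list test.
- **Order control.** Section B3.A.4: "A computer-generated, blocked randomization list will be generated that will randomly assign subjects to one of 6 groups", the six groups being all possible orders of the three treatments. It adds: "The order of drug administration will be counterbalanced to avoid pitfalls of the crossover repeated measures design".
- **Analysis.** Section B3.B, Behavioral Data: "Measures of memory encoding, retrieval and storage will be analyzed using repeated measures ANOVA". No factors are named. The only ANOVA whose factors are described is the hippocampal perfusion analysis under Imaging Data. Its session factor is defined by the three treatment conditions, not by visit number.

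The document mentions no alternate forms, practice session or adjustment for practice.

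**The concern.** Word-list tests can improve with repetition. In a three-period crossover this has two distinct consequences.

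The first is noise. Within a patient, two treatments are compared across different visits, so each paired difference contains the practice gained between those visits. Its sign depends on the order. Balanced orders make it cancel on average, but it still spreads the differences apart. Without a visit term, that spread is counted as error.

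The second is carryover that depends on treatment. Section B2 gives a half-life of 10-11 hours in healthy elderly subjects, so a gap of 168 hours or more is over 15 half-lives and clears the drug. It does not necessarily clear words already learned. The trial expects better memory after drug. If that is true and the same words return, an active session could raise a later placebo session.

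At stake is the precision, and conditionally the size, of the estimated drug effect on a primary outcome in 20 patients. No power calculation is given for this outcome.

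**Working it through.** **The plan's own figure.** The only power stated is 72%, for perfusion. With the B2 table values (0.96, SD 0.29, against 0.77, SD 0.17), the difference is 0.19 and the SD is √((0.29² + 0.17²)/2) = 0.238. For two independent groups of 20, two-sided α of 0.05 (assumed) and a normal approximation: 0.19/(0.238 × √(2/20)) = 2.53, and Φ(2.53 − 1.96) = 0.715. The figure reproduces, but it says nothing about memory.

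**Step 1: average practice bias.** Over the six orders, the visit gap between any two treatments is +1, +2, −1, −2, +1, −1, which sums to 0. Twenty is not a multiple of six. With three full sets of six plus two further patients in different orders (assumed, since block size is not stated), the worst imbalance is (2 + 1)/20 = 0.15 of one visit's gain. Average bias is therefore small.

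**Step 2: noise.** The mean squared visit gap is (4 × 1² + 2 × 2²)/6 = 2. A linear gain δ per visit therefore adds 2δ² to the variance of a paired difference when visit is not modelled. With δ in units of the paired-difference SD (assumed range):

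| δ | Added variance | Added SD |
|---|---|---|
| 0.2 | 2 × 0.04 = 8% | √1.08 − 1 = 4% |
| 0.4 | 2 × 0.16 = 32% | √1.32 − 1 = 15% |

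Equivalently, the inflation is 1 + p², where p is the gain in within-subject SDs (p = √2 × δ, so this range is p = 0.28 to 0.57).

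**Step 3: effect on the test.** Simulation settings: 3,000 runs, 20 patients, blocks of six assumed, both doses 0.95 within-subject SD above placebo, and an ANOVA with patient and treatment, without and with visit.

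| p | Power without visit | Power with visit | Type I error without | Type I error with |
|---|---|---|---|---|
| 0 | 0.86 | 0.85 | 0.050 | 0.050 |
| 0.25 | 0.84 | 0.85 | 0.046 | 0.052 |
| 0.5 | 0.77 | 0.86 | 0.023 | 0.048 |

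For a paired contrast with 80% power at n = 20 and no practice, leaving practice unmodelled gives 78% at p = 0.25 and 71% at p = 0.5. Restoring 80% would need 22 and 25 patients.

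**Step 4: carryover, only if the list is reused.** Let both doses raise recall by 1 unit, and let a fraction k of that gain persist.

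- *Next visit only.* Placebo directly follows an active session in 4 of 6 orders. A given dose directly follows the other dose in 2 of 6. Drug minus placebo = 1 + k/3 − 2k/3 = 1 − k/3.
- *All later visits, without decay.* Placebo is preceded on average by (0 + 0 + 1 + 1 + 2 + 2)/6 = 1 active session, and a given dose by 3/6 = 0.5. Drug minus placebo = 1 + k/2 − k = 1 − k/2.

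| k (assumed) | Shrinkage, next visit only | Shrinkage, all later visits |
|---|---|---|
| 0.1 | 3.3% | 5% |
| 0.25 | 8.3% | 12.5% |
| 0.5 | 16.7% | 25% |

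Across the six orders treatment is balanced over visits, so a visit term leaves this shrinkage unchanged. Only different word content addresses it.

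**The case against.** The strongest reply is that the design already deals with order. All six sequences are used, expressly to counter the problems of a repeated-measures crossover. This stands for average practice bias, which is nearly gone. It does not stand for the error variance, which balance alone leaves inflated.

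A reader might infer from "Visits #1-3 (identical procedures, visit length 5-7 hours" that the same word list is given three times. The documents do not support that. The phrase heads a schedule of steps that also contains the drug infusion, whose content changes at every visit by design. The plan is silent on lists, and form selection may be set out in a test manual that is not part of these documents.

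A reader might also infer that the memory ANOVA definitely excludes visit. That too goes beyond the text. The memory paragraph names no factors. The imaging sentence is loosely worded, since it calls the outcome itself a factor, so it is weak evidence of a complete model. What can be said is that no visit term is specified.

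Finally, these are patients with impaired declarative memory, and the documents give no data on practice or on retention over 1-2 weeks. Both may be small. At p = 0.25 the simulated loss is only about one percentage point of power. This stands, and it is why every size given here is conditional.

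**Conclusion.** The point holds as a gap in specification with a likely cost in precision. For a primary outcome tested three times, the plan should say which list is used at each visit and whether visit enters the model.

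- **Noise.** Under an assumed linear gain of 0.2 to 0.4 paired-difference SD per visit, the variance of a paired difference rises by 8% to 32%. The test becomes conservative and loses power. It would be wrong to read this as a risk of false positives: the simulated type I error falls below 5%.
- **Carryover.** Shrinkage of k/3 to k/2 requires all of three things: list reuse, a real drug-related learning gain, and retention of that gain to later visits. It is not an established bias. If retention is near zero, so is the shrinkage.

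Neither consequence invalidates the trial.

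**What to change.** 1. In Behavioral Data (B3.B), state the memory model: free recall with patient, treatment (three levels) and visit (three levels) as factors. The visit term uses 2 df. In the simulation it cost almost no power when there was no practice effect (0.85 against 0.86), and at p = 0.5 it kept power at 0.86 against 0.77 without it.
2. In Behavioral testing (B3.A.5, item o), specify a different parallel word list at each visit where equivalent forms are available, in the same list order for all participants. In the visit schedule, make clear that identical procedures does not mean identical test content.

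The cost is obtaining the forms and adding a line to each section. With a fixed list order, list difficulty is confounded with visit. That does not affect the treatment contrast, because the visit term absorbs practice and list difficulty together and treatments are close to balanced over visits. It does mean that the visit effect cannot be read as practice alone. If equivalent forms cannot be obtained, the visit term should still be added, and possible carryover of learned words should be stated as a limitation.

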Data on acute use of intravenous levetiracetam in elderly patients is limited. Levetiracetam is well tolerated in healthy young subjects (< 65 years) after 15 minute (2000-4000mg) and 5 minute (1500-2500mg) infusions⁴². One retrospective observational study included 14 older patients (mean age 73.9 years) with a series of complex partial seizures or convulsive or non-convulsive status epilepticus needing emergent intravenous (IV) treatment⁴³. Seizure control was achieved in 11/14 patients (78.6%) at a mean dosage of 1,643 mg/day (range 500-4,000). The only adverse effect was sedation.

Levetiracetam was recently tested in animal models of AD and in adults with mild cognitive impairment. Levetiracetam 5 mg/kg reduced epileptiform discharges and improved memory performance in hAPP mice, while sodium channel blocking AEDs resulted in worsened memory performance. In a recent study in patients with mild cognitive impairment, levetiracetam 250mg twice daily for two weeks normalized hippocampal hyperperfusion, as measured by blood oxygen level dependent (BOLD) MRI. For this study, we chose two doses of levetiracetam (low 2.5 mg/kg and high 7.5 mg/kg) based on the information above.

B3. DESCRIPTION OF RESEARCH PROTOCOL

A. Study Design – Overview, Methods, Procedures

1. Study Overview

This double-blind, within-subject crossover pilot study will test whether increased hippocampal perfusion on ASL-MRI in AD is caused by epileptiform activity. If epileptic activity is occurring and impairing hippocampal function, then levetiracetam should lead to decreased rCBF in the hippocampus and improved declarative memory.

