We will do two analyses, one focused specifically on hippocampal perfusion and a second analyzing regional CBF throughout the whole brain. First, we will use a repeated measures ANOVA with hippocampal perfusion and session (placebo, 2.5mg/kg and 7.5mg/kg) being the factors. Hippocampal perfusion is measured as a percentage of visual cortex perfusion, using a template available within the Statistical Parametric Mapping package. Second, we will measure regional CBF throughout the whole brain using SPM5 and measure changes after drug vs. placebo using a random effects model and accounting for the repeated measures design. In addition to direct analysis of perfusion, we will examine cortical changes in CBF correlated with our seed region in the hippocampus. We predict that decreases in perfusion in the hippocampus after levetiracetam will correlate with increases in perfusion in association cortical regions. Lastly, we will test for correlations between behavioral measures of memory and regional changes in CBF in hippocampus and whole brain. We predict that decreases in hippocampal perfusion will paradoxically correlate with improved declarative memory performance.

EEG Data

EEG will be visually analyzed for presence of epileptiform activity. Peak alpha power, beta band power, delta/theta power, and coherence will be calculated using BESA (Brain Electrical Source Imaging) software and Persyst MagicMarker software. Measures will be analyzed using repeated measures ANOVA. We hypothesize that levetiracetam will decrease source coherence in temporal regions.

Analyses will be performed in the Cognitive Neurology Unit, Magnetic Resonance Imaging Center of the Department of Radiology, and EEG Laboratory at Beth Israel Deaconess Medical Center.

C. Subject Selection

Subjects will be recruited from the Cognitive Neurology Unit at BIDMC. The P.I., who specializes in neurodegenerative disorders, maintains an active clinic and treats over 100 patients with AD. In addition, the Cognitive Neurology Unit has over 13,000 patient visits per year.

Inclusion Criteria:

- Meets the NINCDS-ADRDA criteria for probable Alzheimer's disease
- Mild AD (MMSE \geq 20)
- Age \geq 50 years
- English as first language

Exclusion Criteria:

- A history of seizures prior to the onset of AD
- Familial Alzheimer's Disease due to known genetic mutations
- Current use of an anti-epileptic medication

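### Does the plan need a power statement for memory performance, when its only power figure (72%) is for hippocampal perfusion?

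*Combined protocol and SAP*

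**What the plan says.** In B3, part B (Statistical Considerations), the Sample Size Justification bases its calculation on the group's earlier comparison of AD patients with controls and concludes: "With a sample size of 20 AD participants, we will have a 72% probability of detecting a decrease in perfusion after levetiracetam". The assumed effect is a fall to the control level. The paragraph adds: "This estimate is likely overly conservative for two reasons". The reasons given are the within-subject design and the possibility that the drug unmasks underlying hypoperfusion.

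The Data Analysis list that follows has two primary outcomes, perfusion and "Differences in memory performance". The Behavioral Data paragraph says: "We will test our a priori main hypothesis of improved memory performance after drug". The behavioral testing item of the Study Procedures fixes the measure: "The primary endpoint for memory testing will be the free recall score from the Free and Cued Selective Reminding Test". For perfusion the planned test is stated under Imaging Data: "we will use a repeated measures ANOVA with hippocampal perfusion and session (placebo, 2.5mg/kg and 7.5mg/kg) being the factors". Memory measures are also to be analyzed by repeated measures ANOVA. No section gives an expected change, an SD, a detectable difference or power for free recall.

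**The concern.** A plan that justifies its size by formal power and lists two primary outcomes would normally say what it can detect on each. Here the second has nothing, and the 72% cannot be carried over, because every input to it is a perfusion value. The remark that the estimate is conservative does not help either. The unmasking argument concerns perfusion only, and the within-subject argument cannot be quantified for free recall without a variance or a between-session correlation.

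What is at stake is how a flat memory result would be read. The Study Overview says that if epileptic activity is impairing the hippocampus, "then levetiracetam should lead to decreased rCBF in the hippocampus and improved declarative memory". A reader could take no improvement in memory as evidence against the hypothesis, when a study of 20 may simply have been too small to show a moderate change.

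**Working it through.** **1. The plan's own figure.** Inputs from the table in section B2: AD mean 0.96 (SD 0.29), control mean 0.77 (SD 0.17). The effect is 0.96 − 0.77 = 0.19. Alpha and sidedness are not stated, so two-sided 0.05 is assumed.

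- Standard error for two independent groups of 20: √[(0.29² + 0.17²)/20] = 0.0752.
- Ratio: 0.19/0.0752 = 2.53.
- Power: 71.5% by normal approximation, 69.3% by noncentral t on 38 df.

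The 72% is therefore best read as an unpaired normal-approximation figure. No input is a memory measure.

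**2. Is it conservative for perfusion?** For a paired comparison, SD of the difference = √(s₁² + s₂² − 2ρs₁s₂). With SDs 0.29 and 0.17, paired power reaches 72% at ρ = 0.13. If the post-drug SD is also 0.29, it needs ρ = 0.40. The documents give no ρ, but the claim is reasonable at full normalization.

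**3. What can be said about memory.** Let e be the mean change divided by the SD of the within-patient difference, with 20 completers and two-sided 0.05.

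- One dose v placebo: noncentral t(19), noncentrality e√20.
- Three-session omnibus ANOVA (sphericity, both doses equally effective): noncentral F(2, 38), λ = 20 × (4/3) × e².
- Both doses pooled v placebo (equally effective): noncentral t(19), noncentrality (e/√0.75)√20.

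| True change e | One dose v placebo | Omnibus ANOVA | Pooled v placebo |
|---|---|---|---|
| 0.3 | 24.7% | 24.6% | 31.3% |
| 0.5 | 56.5% | 59.6% | 68.8% |
| Change needed for 80% | 0.66 | 0.63 | 0.57 |

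The 95% confidence interval half-width for one dose v placebo is t(0.975, 19)/√20 = 0.468 SDs of the difference.

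**4. How far these figures depend on the assumptions**, at e = 0.5 for the effective or high dose:

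- Alpha 0.025, one dose v placebo: 44%; the change needed for 80% rises to 0.74.
- 17 completers (assumed), one dose v placebo: 49%.
- Low dose half as effective: 47% for the omnibus ANOVA, 45% pooled.
- Only one dose effective: 23% pooled.

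**5. Conversion to the test's own scale.** This cannot be done. No free-recall SD, correlation or minimum relevant change appears in the documents, so 0.66 cannot be turned into words recalled.

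**The case for a change.** The strongest argument for changing the text is that memory is listed as primary without qualification. The gap therefore does not depend on how the sentence about the main hypothesis is read. That sentence opens the Behavioral Data paragraph and is followed at once by a secondary analysis, so it can mean main among the behavioral tests. Aim 1 concerns perfusion, and Aim 2 frames memory as a correlation with the perfusion change. But the primary outcome list stands on its own. A few sentences would cost nothing, would show that an observed difference of zero is compatible with about half an SD of benefit or harm, and would commit the authors to confidence intervals, which the plan does not promise.

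It stands that the statement is absent and that adding it would be good reporting. It does not stand that the plan is wrong without it. The feared misreading is an inference from the Study Overview; no section says that a non-significant memory result will be treated as no effect. A standardized figure would also leave the practical question open, since the reader still could not tell whether a worthwhile change in free recall is detectable. And a single figure could mislead in its turn: the range of 56% to 69% at 0.5 SD holds only with equally effective doses, 20 completers and no allowance for two primary outcomes.

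**Conclusion.** No change is needed. The sample size text is silent on one of two primary outcomes, but this is a missing detail and not an error. The "72% probability of detecting a decrease in perfusion after levetiracetam" reproduces (71.5%) and is a fair, probably conservative, figure for perfusion at full normalization. Sizing a mechanistic pilot on the outcome with earlier data is a defensible choice, and the patient number, endpoints and repeated measures analyses would be the same with or without a memory statement.

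The size of what is unsaid is about 0.66 SDs of the within-patient difference for 80% power on one dose against placebo (0.74 at alpha 0.025), with a 95% interval of about ±0.47 SD. This assumes 20 completers and a two-sided test. Fewer completers lower the power, and unequal dose effects lower it for the omnibus and pooled comparisons. Analysts reporting free recall can be expected to give dose-placebo differences with confidence intervals from data already collected, and to read a null memory result as inconclusive for moderate effects.
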